breastfeeding mother and the baby. Ketamine and its metabolites will be evaluated in PND patients receiving ketamine 0.5 mg/kg or 0.2 mg/kg at 30 mins, 2 hours and 4-5 hrs after ketamine infusion. All adverse medical and psychiatric events with onset or worsening after the administration of ketamine will be included in the analysis.

The proposed experiment will be a proof-of-concept study in which we will evaluate the safety, pharmacokinetics, and efficacy of ketamine 0.5 mg/kg and 0.2 mg/kg over 40 minutes in a double-blinded and crossover fashion separated over one week (5) (dose used in antidepressant clinical trials) in PND patients who are not currently breastfeeding. The primary outcome measure of efficacy will be the Hamilton Depression Rating Scale (HAM-D-17) at 24 hours and additional secondary anxiety and mood scales. (6). Any adverse medical and psychiatric events will be recorded and summarized. Ketamine and its metabolites will be evaluated at 30 mins, 2 hours and 24 hrs.

Hypothesis 1): Ketamine will significantly decrease (>50%) in HAM-D17 scores at 24 hrs after infusion from baseline. The 0.5 mg/kg dose will be more efficacious than 0.2 mg/kg in improving depression symptoms.

Hypothesis 2) Ketamine will improve anxiety symptoms in PND (as measured using HAM-Anxiety and EPDS) at 24 hrs after infusion in patients with PND. Anxious subtypes are the most common subtype during a late postpartum period representing about 70 % of PND. (40)

Hypothesis 3) Ketamine infusion will be tolerated well by the patients with fewer side effects at 0.2 mg/kg compared to 0.5 mg/kg.

METHODS

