Research Design and Methods: All human subjects' research will be conducted with full approval from the IRB at the University of Texas Health Science at Houston. We will recruit PND patients (N=10) who will be administered a single intravenous infusion of Ketamine either at 0.5 mg/kg or 0.2 mg/kg over 40 minutes in a double-blinded and crossover fashion separated by minimum 7 days, with the order being randomized and balanced across subjects. Two doses will help decide the safe, tolerable and effective dose for PND subjects will undergo a standard screening interview visit to confirm eligibility evaluations including SCID-4 interview (27) and collection of demographic, clinical and medical history. To ensure medical stability, each patient will have a physical examination and urine toxicology screen to rule out the recent undisclosed use of illicit substances. It will also be requested that the patient provide a record of lab results to indicate adequate health for inclusion.

We will pre-screen potential participants over the phone to minimize the invitation to non-eligible participants. Eligible patients that want to participate in the study will be scheduled to have a screening visit to review consent and determine eligibility.

The total duration of the commitment of the study is minimum of 4 weeks. Extension of the timeline can occur depending on the time between the screening visit and the first infusion dose. The total commitment should not exceed 3 months. There will be a minimum 7 days between the 2 infusions. Patients who qualify will complete the infusions on another day at UTHealth Clinical Research Unit at Memorial Hermann-TMC, Houston. University of Texas Health Science Center at Houston Memorial Hermann-TMC [name] or at our Harris County Psychiatric Center (HCPC) where they will be given the ketamine infusion by the study nurse. Patients will be advised to follow the American Association Preoperative Fasting Guidelines prior to infusion.

There will be two appointments where they will be administered a single intravenous infusion of Ketamine either at 0.5 mg/kg or 0.2 mg/kg over 40 minutes in the first infusion visit and a second infusion visit where they will receive the infusion that was not given on the first visit, where there will be a minimum of 7 days between infusions.

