DATA ANALYSIS PLAN - General Data Analysis: The data analytic strategy will use generalized linear modeling. Statistical analyses will use SAS v.9.3. Preliminary data analyses will inspect baseline, treatment from baseline differences as well as correlations between baseline variables and specified outcomes. Baseline characteristics will be compared within groups using Student's t-tests for continuous data and chi-square tests for categorical data.

Sample size justification: our power calculation is guided by a previous study - intravenous ketamine in TRD patients (28) with effect size (Cohen's $d = 1.46$) or Brexanolone in PND (effect size 1.2) (12, 32). For an effect size 1.2, a total of 10 PND patients will be required for within-subject design with probability 95 % that the study will detect a treatment difference at a one-sided 0.05 significance level.

Hypothesis: Based on previous studies (33, 34) and our pilot Ketamine TRD patient data, we predict that ketamine infusion compared to baseline will significantly decrease HAM-D scores in PND patient at 24 hrs. The severe anxious subtype will have prominent improvement.

Analysis: We will use linear regression to assess associations between improvements in depressive symptoms (change in the HAM-D from baseline using LOCF). A paired t-test was performed to evaluate the key efficacy measure - change from baseline in HAMD total score. We will also perform a secondary analysis comparing change from baseline to endpoint using last observation carried forward (LOCF) using a paired sample t-test. Secondary outcomes are safety and tolerability measures, including treatment-emergent AEs and changes from EPDS, GAD-7, PHQ-9, and C-SSRS. We will also investigate specific markers for treatment response.

Alternate plans: The proposal applies the widely used ketamine sub-anesthetic dose (0.5 mg/kg) as a treatment for PND. If the effect is less clear or patient experiences any adverse effects, alternate strategies will be explored (two doses of ketamine instead of single or low dose 0.3 mg/kg if adverse effects etc. respectively). Patient safety and tolerability will be the most important guiding principle. This will require an amendment in the protocol and an updated consent.

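### The analysis plan tests HAM-D only against baseline, so the dose part of Hypothesis 1 (0.5 versus 0.2 mg/kg), the trial's only randomised efficacy comparison, has no stated analysis

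*Combined protocol and SAP*

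**What the plan says.** **Aims and design.** Under PRIMARY HYPOTHESES AND SPECIFIC AIMS, Hypothesis 1 has two parts. The first is "Ketamine will significantly decrease (>50%) in HAM-D17 scores at 24 hrs after infusion from baseline". The second is "The 0.5 mg/kg dose will be more efficacious than 0.2 mg/kg in improving depression symptoms". METHODS (Research Design and Methods) gives both doses to each of 10 patients in a "double-blinded and crossover fashion separated by minimum 7 days, with the order being randomized and balanced across subjects", and says that the two doses are there to help choose a safe, tolerable and effective one. JUSTIFICATION explains the absence of a placebo group by the aim of finding out whether the lower dose matches the higher one in effect with fewer side effects.

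**Analysis.** Under DATA ANALYSIS PLAN, the Hypothesis paragraph reads "we predict that ketamine infusion compared to baseline will significantly decrease HAM-D scores in PND patient at 24 hrs". The Analysis paragraph names the key test: "A paired t-test was performed to evaluate the key efficacy measure - change from baseline in HAMD total score". The secondary efficacy analysis is one "comparing change from baseline to endpoint using last observation carried forward (LOCF) using a paired sample t-test". There is also a regression: "We will use linear regression to assess associations between improvements in depressive symptoms (change in the HAM-D from baseline using LOCF"; no predictor is given. A general sentence refers to generalized linear modelling without naming an outcome, a term or a contrast.

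**Sample size.** Ten patients are required for an effect size of 1.2 in a within-subject design, "with probability 95 % that the study will detect a treatment difference at a one-sided 0.05 significance level".

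**The concern.** Dose order is the only thing randomised. A fall in HAM-D from baseline to 24 hours has no control, so it mixes drug effect with expectation, regression to the mean and the natural course of the episode. The difference between doses within a patient is protected by the randomisation and the blind, and the analysis text never mentions it.

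Three things are at stake. First, the model for the dose comparison, including whether it allows for period, would be chosen after the data are in. Second, HAM-D-17 is scheduled at screening and before each infusion, so baseline could mean either, and the plan does not say which. Nor does it say that last observation carried forward stays within one infusion period; if it does not, a score obtained after one dose could stand in for a missing score after the other. Third, Hypothesis 1 expects the higher dose to be better, while JUSTIFICATION asks whether the lower dose is as good, with no margin. A null dose result could be read as failure of the first or as support for the second.

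**Working it through.** **Step 1: hypothesis against analysis.**

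| Element | Dose contrast named? |
|---|---|
| Hypothesis 1, second part | Yes: 0.5 better than 0.2 mg/kg |
| Crossover design in METHODS | Yes: the two doses are what is randomised |
| Hypothesis paragraph of the analysis plan | No: ketamine compared with baseline |
| Key paired t-test | No: change from baseline |
| Secondary LOCF paired t-test | No: baseline to endpoint |
| Linear regression | No: no predictor stated |
| Generalized linear modelling | No: no outcome, term or contrast stated |

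No other section supplies a 0.5 versus 0.2 mg/kg analysis of HAM-D-17. The doses named in the analysis plan are 0.5 and 0.3 mg/kg, both under Alternate plans.

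**Step 2: the plan's own figure.** Inputs from Sample size justification: effect size d = 1.2, one-sided alpha 0.05, 95% power. For a paired t-test, power = P(T > t(0.95; df)), where T is noncentral t with noncentrality d√n and df = n − 1.

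- n = 9: noncentrality 1.2 × √9 = 3.60, 8 df, power 94.8%.
- n = 10: noncentrality 1.2 × √10 = 3.79, 9 df, power 96.7%.

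So N = 10 reproduces.

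**Step 3: does that identify the comparison?** Treat 1.2 instead as a standardised within-patient dose difference, with a period term (df = n − 2). Power is 94.3% at n = 9 and 96.4% at n = 10, so N = 10 again. The arithmetic fits both readings. Only the wording (compared to baseline, change from baseline) ties the stated power to the pre-post question.

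**Step 4: what N = 10 gives for dose.** The documents state no between-dose effect, so the standardised within-patient difference δ (mean difference divided by the SD of the difference) is an assumption. With dose, period and patient in the model there are 10 − 2 = 8 df. Noncentrality is δ√10 and the one-sided 0.05 critical value is 1.860.

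| Assumed δ | Noncentrality | Power |
|---|---|---|
| 0.3 | 0.95 | 22% |
| 0.5 | 1.58 | 42% |
| 0.8 | 2.53 | 75% |
| 1.2 | 3.79 | 96% |

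The half-width of the 95% CI is t(0.975; 8)/√10 = 2.306/3.162 = 0.73 SD of the difference. Even an observed dose difference of exactly zero would leave true differences of up to 0.73 SD in either direction inside the interval.

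**Step 5: cost of a period term.** Without it (9 df) power is 43% at δ = 0.5 and 75% at δ = 0.8; with it, 42% and 75%. The loss is under one percentage point in each case.

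**The case against.** **The pre-post test may be the right key test.** JUSTIFICATION gives the primary goal as evaluating safety and efficacy of sub-anesthetic ketamine, and the study is described as proof-of-concept and pilot. The pre-post test addresses that goal and the first part of Hypothesis 1. This stands, and it is why the pre-post test should stay. It does not cover the second part, which the protocol states as a hypothesis and randomises for.

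**The paired t-test may have been meant as a dose contrast.** The sample size sentence speaks of a within-subject design and a treatment difference. That reading is possible but strained: the sentence naming the test and the hypothesis above it both refer to baseline, and 1.2 is given as a brexanolone figure, not as a difference between two ketamine doses. If a dose contrast was intended, the text still has to say so.

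**Stronger readings that the documents do not support.**

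- A reader might take N = 10 as proof that the power calculation is pre-post. Step 3 shows that it fits either comparison.
- A reader might infer from the title of reference 32 that 1.2 is an open-label effect. The plan cites references 12 and 32 together, and reference 12 is not in the list available, so this is not established.
- A reader might say that the whole handling of the pre-infusion score is open. It is not: the plan fixes the measure as change from baseline. Only which baseline is open.
- A reader might say that the plan ignores the 50% in Hypothesis 1. The figure is a parenthetical expected size, and METHODS (Clinical measures) already defines response as 50% improvement.

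**Conclusion.** The concern holds as an omission that can be read directly from the text and does not depend on any calculation. As written, the plan gives an uncontrolled pre-post result, no test of the dose part of Hypothesis 1, and no statement of which baseline defines change.

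The size of the gap in power depends on an unstated between-dose effect. At N = 10 and one-sided 0.05, power is 42% if the standardised within-patient difference is 0.5 and 75% if it is 0.8; both values are assumptions. The CI half-width of 0.73 SD of the difference assumes complete data and 8 df. No HAM-D SD is given, so this cannot be turned into scale points from the documents.

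It does not follow that the sample size is wrong or that the trial cannot inform on dose. The design supports the comparison, and N need not change if the dose result is presented as an estimate.

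**What to change.** Add to the Analysis paragraph:

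1. **Dose contrast, second part of Hypothesis 1.** The within-patient 0.5 minus 0.2 mg/kg difference in change in HAM-D-17, from that infusion's own pre-infusion score to 24 hours. Fit a model with dose and period as fixed effects and patient as random effect (8 df with complete data), and report the estimate with its 95% CI.
2. **Sensitivity.** The same contrast on the raw 24-hour score. If unequal carry-over persists to 24 hours after the second infusion, it biases the raw contrast; if it is present before that infusion but gone by 24 hours, it biases the change contrast. Neither is safe in both cases. The minimum gap is 7 days, and the Aims text itself cites response lasting to one week in up to 35% of treatment-resistant patients.
3. **Missing scores.** Do not carry a score from one infusion period into the other.
4. **Pre-post test.** Keep it as the key test, computed for each dose against that infusion's own pre-infusion score and labelled uncontrolled. This makes two tests at one-sided 0.05 (chance of at least one false positive at most 2 × 0.05 = 10%), so state in advance how they carry the key claim.
5. **Power statement.** Say that the 95% power at 1.2 refers to the comparison with baseline and that no between-dose effect was available. Give the 42% and 75% figures with their assumptions, and the CI half-width.
6. **Aim.** Reconcile Hypothesis 1 with JUSTIFICATION, and state that a non-significant dose difference will not be reported as equal efficacy.
7. **Schedule.** Confirm that HAM-D-17 is taken in the day-1 call after both infusions. In the text available, the assessment table is broken (seven marks for HAM-D under eight columns), and the METHODS text on the calls mentions only mood questionnaires.

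**Cost.** Text changes only, with no new visits or patients if item 7 is confirmed. The period term uses one degree of freedom (43% to 42% power at δ = 0.5). The other price is presentational: the stated precision for dose is less favourable than the pre-post power.

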Clinical studies of Ketamine in depression: The serendipitous discovery of the rapid antidepressant effect of ketamine, a widely used anesthetic drug, has opened up development of novel glutamate-based antidepressant treatment strategies. Sub-anesthetic dose (0.5 mg/kg over 40 minutes) of ketamine improves depression symptoms in patients with TRD (4, 5, 13), bipolar depression (14) and post-traumatic stress disorder (15) and also in reducing suicidal ideation (SI) in depressed patients (16, 17). The improvement in depression scores was seen as early as 2 hours; with 71 % of patients deemed as responders at 24 hours (defined as 50% improvement on 21 items HDRS) and the antidepressant effects persisted in up to 35% of the patient at the end of 7 days (4). A subsequent study found that **early antidepressant response to the first infusion was highly predictive of a sustained response to subsequent infusions** (18). Ketamine improved depression symptoms in patients with anxious depression with a longer time to relapse than those with nonanxious depression (19). In summary, ketamine's beneficial effects on mood and suicidality are very promising but further research is required to understand the ketamine's rapid antidepressant effect. The exact underlying neural mechanisms involved in ketamine's rapid antidepressant effect is currently unclear (20). Emerging evidence suggests that ketamine induces early increases in the excitatory synaptic drive through glutamate activity likely through AMPA and initiates synaptic plasticity processes in cortico-limbic regions presumably mediating the antidepressant effects (21, 22).

Preliminary Studies: To assess the safety, pharmacokinetics and antidepressant efficacy of a sub-anesthetic dose of intravenous ketamine in depression. We studied the effect of ketamine in five patients (n=5) with TRD who received a single intravenous infusion dose of ketamine (0.5 mg/kg) for 40 mins. Four out of five patients successfully responded to ketamine at 24 hrs and tolerated ketamine well; thus supporting the feasibility of the procedure. However, the therapeutic effect of ketamine has not been studied in PND.

PRIMARY HYPOTHESES AND SPECIFIC AIMS

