Severe Perinatal Depression (PND) is a major depressive episode that occurs during pregnancy or onset within 12 months of the birth of a child. The prevalence of severe PND in the general population is estimated to be 5-10% (2). PND is a seriously disabling condition and can increase the risk of self-harm and health complications in mother can deleteriously affect the cognitive, emotional and social development of the child and increases the substantial economic burden on families and society (3). Selective Serotonin Reuptake Inhibitors (SSRIs) and psychotherapy are the main available treatment modalities for PND. While they are effective in some, it takes longer to work and half of the patients do not fully recover from depression. A faster onset of antidepressant action will be critical in enabling faster relief from depression and may increase the chance of full recovery. The main objective of this study is to investigate the rapid antidepressant effect of low sub-anesthetic dose of ketamine in PND.

Aims

To assess the safety, pharmacokinetics and antidepressant efficacy of a sub-anesthetic dose of intravenous ketamine in perinatal depression

A single, intravenous, sub-anesthetic dose of ketamine in patients with Treatment-Resistant Depression (TRD) induces a significant (50%) reduction in depression symptoms within 2 hours of administration with 65% of depressed patients respond by 24 hours and up to 35% maintain response until the end of 1 week (4). Our in-house pilot data, in consistent with worldwide studies, show that ketamine (N=5) can be safely administered to depressed patients and improves depression symptoms when assessed at 24 hrs post infusion. Ketamine has not been studied in the treatment of PND where there is a significant unmet need.

The dosing of ketamine (0.5 mg/kg over 40 mins) for antidepressant treatment was developed from research studies in the 1990s based on use in healthy participants (36). However, newer studies show some patients respond to lower dose and tolerated better (fewer side effects) by the patients (37). IV Ketamine reaches a peak within a few mins with an elimination half-life of 2–3 hrs (38). Ketamine's clearance may be 20% higher in women than in men (39). Ketamine is mostly metabolized in norketamine (80%) and persists more than 5 h after administration (38). It is important to evaluate ketamine's pharmacokinetic data in PND to improve safety for the

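### LOCF is named for two HAM-D analyses, one running to an undefined endpoint, although the protocol cites a fading response; and no dose contrast is written out for Hypothesis 1

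*Combined protocol and SAP*

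**What the plan says.** **LOCF.** The Analysis paragraph of the DATA ANALYSIS PLAN names three HAM-D analyses:

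- a linear regression on "change in the HAM-D from baseline using LOCF";
- a paired t-test for the key efficacy measure, with no LOCF stated;
- a secondary analysis "comparing change from baseline to endpoint using last observation carried forward (LOCF) using a paired sample t-test".

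**Time points.** The Aims fix the primary one: "The primary outcome measure of efficacy will be the Hamilton Depression Rating Scale (HAM-D-17) at 24 hours". Endpoint is not defined anywhere. Research Design and Methods and the schedule of assessments have telephone follow-up on day 1 after infusion 1 and on days 1 and 7 after infusion 2. Medical Monitoring instead lists days 1, 2 and 7 post-infusion. As the schedule reads, HAM-D is marked both before and after each infusion.

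**Expected course.** On treatment-resistant depression, the clinical background reports improvement as early as 2 hours, "with 71 % of patients deemed as responders at 24 hours", and that "the antidepressant effects persisted in up to 35% of the patient at the end of 7 days". The Aims give "with 65% of depressed patients respond by 24 hours and up to 35% maintain response until the end of 1 week", citing the same reference.

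**Dose comparison.** Hypothesis 1 adds: "The 0.5 mg/kg dose will be more efficacious than 0.2 mg/kg in improving depression symptoms". The design is a randomized, balanced two-period crossover with at least 7 days between infusions. JUSTIFICATION cites the comparison with the lower dose as the reason for having no placebo group. The analysis plan opens with "The data analytic strategy will use generalized linear modeling" but lists no model terms, and its own hypothesis is ketamine against baseline.

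**The concern.** LOCF treats the last recorded score as if it still held at the later time. Where response is expected to fade, a 24-hour score carried to day 7 can make a passing benefit look lasting. Patients hospitalized for worsening are removed from the study (Unanticipated Hospitalizations), so relapsed patients are a plausible source of missing day-7 scores. With 10 patients, each carried score is a tenth of the data.

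The dose comparison is a separate gap. Infusion 2 may follow infusion 1 by only 7 days, so some effect of the first dose may remain. The estimate for Hypothesis 1 then depends on which score serves as the infusion-2 baseline. The plan leaves that choice open until after the data are seen.

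**Working it through.** **1. The plan's own figure.** For a paired t-test with effect size 1.2 and one-sided 0.05, noncentral-t power is 94.8% at n = 9 and 96.7% at n = 10. The stated N = 10 for 95% power reproduces. No effect size for a 0.5 v 0.2 mg/kg difference is given.

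**2. If endpoint is day 7.** The documents give responder shares, not mean changes, and no dropout rate, so the inputs are assumptions: 24-hour mean fall 10 points; fraction of the mean effect retained at day 7 either 0.35 or 35/65 = 0.54 (true day-7 fall 3.5 or 5.4); m = 1 to 3 of 10 day-7 scores missing; between-patient SD 4; error SD 3.5.

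When missingness is unrelated to outcome, LOCF reads [(10 - m) × true + m × 10]/10:

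- true 3.5: 3.5 + 0.65m = 4.15, 4.80, 5.45
- true 5.4: 5.4 + 0.46m = 5.86, 6.32, 6.78

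The other patterns were simulated (20,000 trials per case). The mixed model is a random-intercept model on observed scores.

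| Day-7 scores missing in | LOCF, true 3.5 | Mixed model, true 3.5 | LOCF, true 5.4 | Mixed model, true 5.4 |
|---|---|---|---|---|
| least improved at 24 h | 3.8-4.7 | 3.5 | 5.5-6.0 | 5.4 |
| unrelated | 4.15-5.45 | 3.5 | 5.9-6.8 | 5.4 |
| most improved at 24 h | 4.5-6.2 | 3.5 | 6.2-7.6 | 5.4 |
| largest loss by day 7 | 4.9-7.0 | 4.1-5.1 | 6.6-8.3 | 6.0-6.9 |

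In responder terms with unrelated missingness, 0.35 × (10 - m)/10 + p × m/10 turns a true 35% into 38.0-44.0% (p = 0.65) or 38.6-45.8% (p = 0.71).

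**3. If endpoint is 24 hours.** The last score before a missing 24-hour score would usually be the same-day after-infusion HAM-D. It may already hold some, all or more of the 24-hour effect, so the direction of bias is unknown. Only if that score is missing too is a pre-infusion score carried. A 10-point fall then reads 10 × (1 - m/10) = 9, 8 or 7.

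**4. Why the infusion-2 baseline matters.** Assume effects of 10 and 6 points (true contrast 4.0) and 35% of the first effect still present at infusion 2.

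- Entry baseline, effects add. 0.5 mg/kg first: 10 - (6 + 3.5) = 0.5. 0.2 mg/kg first: (10 + 2.1) - 6 = 6.1. Mean 3.3.
- Pre-infusion baseline, effects do not add. 0.5 first: 10 - (6 - 3.5) = 7.5. 0.2 first: (10 - 2.1) - 6 = 1.9. Mean 4.7.
- The other two combinations average 4.0.

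The shift is half the retained fraction times the dose difference: 0.5 × 0.35 × 4 = 0.7. Balanced order cancels equal residual effects, not unequal ones, and a period term leaves the complete-data contrast unchanged. The standard error is √(2 × 3.5²/10) = 1.57 with the entry baseline and √(4 × 3.5²/10) = 2.21 with each infusion's own baseline.

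**5. Which mixed model.** With the same effects, no carryover, and day 7 observed after infusion 2 only, a model with dose, period and time but no dose-by-time term forces one dose difference on both times. Its 24-hour contrast is about 3.3 (35% retained) or 3.5 (54%) against a true 4.0. Fitting 24-hour scores only, or adding dose-by-time, returns 4.0.

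**The case against.** **LOCF is confined to secondary analyses.** This stands. A reader might infer that the primary 24-hour result is contaminated, but the documents do not attach LOCF to the key paired t-test. What that test lacks is any rule for a missing 24-hour score. The figures above concern the mean-change test; no effect on the regression has been shown.

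**The fading argument needs endpoint to mean day 7.** This also stands, since the plan does not say so. It is equally tempting to claim that LOCF at 24 hours pulls the result toward no change. The scheduled after-infusion HAM-D undercuts that as a general claim. The 9-7 figures need that score missing as well, which is possible because the protocol says only that questionnaires may be completed after the session.

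**LOCF is not always the worse estimator.** Correct. When the least improved patients are missing, its root mean squared error is slightly smaller at 54% retained for one to three missing, and no worse at 35% retained for one or two missing (1.57 v 1.62 with one). In the worst pattern it is much larger (3.84 v 2.32). That pattern assumes no patient-to-patient variation in true response, so the patients who lost most are picked out by error alone.

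**The general model may be meant to cover dose.** It may, but no terms are written. Nor is dose the only aim: JUSTIFICATION also names safety and efficacy as the primary goal, and the stated main objective is the rapid antidepressant effect. That limits the weight of the gap but does not close it, because Hypothesis 1 makes the dose claim explicitly.

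**Conclusion.** The point holds as a should-fix, with medium confidence. LOCF is prescribed for two HAM-D analyses, one to an undefined endpoint, with conflicting contact days. If endpoint is day 7, LOCF tends to overstate lasting benefit. Under the stated assumptions a true 3.5-point fall reads about 3.8 to 7.0, and a true 5.4-point fall about 5.5 to 8.3. These sizes rest on assumed effects, SDs, retained fractions and missing counts. If endpoint is 24 hours, no direction can be given.

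Separately, Hypothesis 1 has no written contrast, period term or infusion-2 baseline. Under the assumed effects the baseline choice can move a true 4.0-point contrast to 3.3 or 4.7.

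Three stronger inferences are not supported: that the stated sample size is wrong (it reproduces for a paired t-test), that the data needed for the dose contrast are not collected (HAM-D is scheduled before and after each infusion), and that a mixed model removes all bias (it does not when patients leave after an unrecorded relapse).

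**What to change.** Amend the analysis plan as follows.

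- Delete LOCF. Carry no score across time points or from one infusion to the other.
- Tie endpoint to a stated time point, and reconcile the contacts in Research Design and Methods and the schedule with those in Medical Monitoring.
- Keep the key paired t-test of 24-hour change from baseline on observed scores, and state how a missing 24-hour score is handled.
- For Hypothesis 1, fit the 24-hour HAM-D-17 scores only, in a mixed model with random patient, fixed dose and period, and small-sample degrees of freedom (for example Kenward-Roger). State the 0.5 v 0.2 mg/kg contrast.
- Fix the main baseline in advance, for example the pre-infusion-1 HAM-D for both infusions. Use change from each infusion's own pre-infusion HAM-D as a supportive sensitivity analysis only; with 10 patients the two versions cannot reliably detect a 0.7-point shift.
- If day 7 enters the model, include a dose-by-time term. Under the contacts in Research Design and Methods, a day-7 dose comparison is 5 v 5 between patients and should be descriptive.
- State that the period term does not remove unequal carryover, and report the reason for each missing HAM-D.

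Cost: plan wording and a little more analysis, with no new data. Under the assumed SDs the standard error of the day-7 mean is about 1.6-1.8 instead of 1.5-1.6 with LOCF, and in the favourable patterns noted above LOCF's total error would have been slightly smaller. No change to doses or to the infusion interval is proposed.
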